7. STATISTICS AND DATA ANALYSIS

Baseline data will be taken from the first 14 days of monitoring and outcomes will be calculated from the last 30 days of the treatment period.

Power calculation: Based on findings from our 'I HART CGM trial', we would expect percentage time spent in hypoglycaemia (<3.0mM) to be 64% lower in the CGM group compared to the self-monitoring group [mean (SD): CGM group 2.1% (2.3%); self-monitoring group 5.8% (5.9%)]. To demonstrate that difference as significant at $p<0.05$ and with 80% power, 25 participants would be needed in each group. To allow for a 10% drop-out 55 participants will be recruited.

Analysis: Intention to treat. The primary outcome will be assessed by two-tailed unpaired t-test. For secondary outcomes, parametric data will be compared between the two study arms by two-tailed unpaired t-test for continuous variables. Non-parametric data will be compared using a Wilcoxon Rank sum test.

Sub-analysis: Other outcomes assessed will include hypoglycaemia awareness by participant (Gold score). Hypoglycaemia outcomes will be assessed throughout the time period and nocturnal only.

Data and all appropriate documentation will be stored for a minimum of 10 years after the completion of the study, including the follow-up period.

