2. STUDY OBJECTIVES

Primary outcome: % time spent in hypoglycaemia (<3.0mmol/L, 55mg/dL)

Secondary outcome: Number of episode of serious hypoglycaemia (defined as a sensor glucose <3.0mmol/L (55mg/dL) for >20 minutes)

% time spent in hypoglycaemia (<3.9mmol/L, 70mg/dL)

% time in euglycaemia (3.9-7.8mmol/L, 70-140mg/dL)

% time spent in target (3.9-10mmol/L, 70-180mg/dL)

% time spent in hyperglycaemia (>10mmol/L, 180mg/dL)

Number hypoglycaemic excursions

Severe hypoglycaemia

MAD%

Glucose variability

HbA1c

Ambulance call-out rates

Diabetes treatment satisfaction questionnaire

CGM usability

PAID

Gold score

Fear of hypoglycaemia survey score (HFS2)

Cost effectiveness

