6. ASSESSMENT AND FOLLOW-UP

6.1 CLINIC VISIT 1: Screening and Randomisation

Following informed consent study participants will give a full medical and medication history, as well as undergo a physical examination and ECG. Venous blood tests will be taken and sent to assess HbA1c, plasma glucose, renal function, serum C-peptide, thyroid function test, 9 am cortisol and coeliac screen (tissue transglutaminase antibody). Women of childbearing age will have a urine pregnancy test. If participants meet the inclusion criteria they will be enrolled on to the study and will complete a semi-structured participant interview and questionnaires (Diabetes treatment satisfaction questionnaire, CGM usability, PAID, and Fear of hypoglycaemia survey score (HFS2)). A Gold Score questionnaire will also be completed.

Participants enrolled will be randomised to real-time continuous glucose monitoring (RT CGM) or self-monitoring blood glucose (SMBG) group. Randomisation will be done using sealedenvelope.com and stratified by insulin delivery modality.

The RT CGM group will receive a Dexcom G6 transmitter and sensors, as well as a structured education refresher focusing on hypoglycaemia avoidance, recognition, and management. Participants in the SMBG group will receive the same structured education refresher focusing on hypoglycaemia avoidance, recognition, and management. All education will be delivered by the research nurse from a predefined curriculum and will be supported by independent written materials.

Participants will be instructed to test their capillary blood glucose if symptoms of hypo- or hyperglycaemia occur, in case of sensor failure or if the sensor glucose is out of the desired range. Participants using the G6 sensor will change sensor every ten days (or sooner in the event of sensor failure). Low glucose alert settings will be standardised at 4.4 mmol/L (80mg/dL) for all participants at the start of the study and can be reduced to 4 mmol/L (70mg/dL) at week 2 during the telephone visit depending on participant preference. High glucose alerts may be personalised.

The SMBG group will additionally undergo blinded CGM at weeks 1 and 2, weeks 4 to 6 and weeks 9 to 12 using the Dexcom G6 system. Participants in this group will be shown how to insert the Dexcom G6 at the first clinic visit and sensors provided so they can do this at home.

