6.2 FOLLOW-UP: Telephone follow-up during study period

Participants will be provided telephone support twice in the first week, then weekly for the next 3 weeks, and every 2 weeks thereafter, to optimise glucose and reduce the risk of further hypoglycaemia.

Participants in the CGM group with an iOS or Android smartphone will be able to upload and share data with the Research team through the “Dexcom Share app”. Participants who do not have a smartphone can upload their CGM data to an online platform named “Tidepool” using a PC or Mac desktop computer. In total, participants will use CGM for 12 weeks.

Participants in the SMBG group will be asked to self-monitor a minimum of 4 times daily and upload data to Tidepool, an online not-for-profit platform for individuals to selectively share data with clinicians to optimise diabetes management. They will receive telephone support from the research team, based on their Tidepool data, at the same time points as the RT-CGM group to optimise glucose and reduce the risk of further hypoglycaemia. Blinded CGM data from the SMBG group will be uploaded at the end of week 2, end of week 6 and end of week 12.

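### The 30-day outcome window begins two days before the SMBG arm's last blinded CGM block, so raw episode counts would cover 30 days in one arm and 28 in the other

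*Combined protocol and SAP*

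**What the plan says.** Section 7 sets both analysis windows. For baseline, "Baseline data will be taken from the first 14 days of monitoring"; for the endpoint, "outcomes will be calculated from the last 30 days of the treatment period". Section 3.3 gives each participant 12 weeks.

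Sensor coverage differs by arm. For RT-CGM, section 6.2 says "In total, participants will use CGM for 12 weeks". For the control arm, section 6.1 says "The SMBG group will additionally undergo blinded CGM at weeks 1 and 2, weeks 4 to 6 and weeks 9 to 12", and section 6.2 has those data "uploaded at the end of week 2, end of week 6 and end of week 12". Section 6.1 also says "Participants using the G6 sensor will change sensor every ten days".

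Section 2 lists among the secondary outcomes "Number of episode of serious hypoglycaemia (defined as a sensor glucose <3.0mmol/L (55mg/dL) for >20 minutes"), and separately a number of hypoglycaemic excursions. Neither has a time denominator, and section 7 has no rule for adjusting to sensor wear. For the test, section 7 says "Non-parametric data will be compared using a Wilcoxon Rank sum test".

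**The concern.** The endpoint window is longer than the sensor block that has to supply it in the SMBG arm. An analyst who follows section 7 literally takes 30 days of sensor data from RT-CGM participants and can find at most 28 scheduled days in SMBG participants.

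This hardly matters for a percentage of time, which is already scaled to the time observed. It matters for a count, because longer observation gives more events at the same underlying rate. Two secondary outcomes are at stake: serious sensor episodes, which section 2 defines from sensor glucose, and hypoglycaemic excursions, where a sensor basis is an inference. The primary outcome, the other percentage-of-time outcomes and the sample size do not depend on the point.

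**Working it through.** **Calendar**

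- Treatment period: 12 × 7 = 84 days (section 3.3).
- Last 30 days: 84 − 30 + 1 = 55, so days 55 to 84 (section 7).
- Week k covers days 7(k − 1) + 1 to 7k. Weeks 9 to 12 are therefore days 57 to 84, or 28 days (section 6.1).
- Check on the numbering: weeks 1 and 2 are days 1 to 14, which matches the 14-day baseline in section 7.
- Days in the window without scheduled SMBG sensor data: days 55 and 56.
- Planned sensor days in the window: RT-CGM 30, SMBG 28. Ratio of expected raw counts at equal true rates: 30/28 = 1.071.

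If weeks 9 to 12 meant the end of week 9 to the end of week 12, coverage would be 21 days and the ratio 30/21 = 1.43. The 28-day reading is the milder one and fits the baseline numbering.

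**Sample size per arm used below**

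The plan's 25 per group is broadly reproduced. The difference is 5.8 − 2.1 = 3.7 and the SD is √((2.3² + 5.9²)/2) = 4.478. Two-sided 5% and 80% power give 23 per group by the normal approximation, 24 by the t-test and 25 by the Welch t-test. The window problem does not touch this figure.

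**Effect on the test**

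The documents give no episode rate, so the rates and between-person CVs here are assumptions. Counts are gamma-Poisson, with 25 per arm, 20,000 runs per cell, and a two-sided, tie-corrected Wilcoxon test at 0.05. A ratio of 0.36 is the plan's 64% reduction in time below 3.0 mmol/L, applied to episodes as an assumption. A ratio of 0.50 is assumed outright. Each cell shows the rejection rate with 30 v 28 days, then with 28 v 28 days.

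| Episodes/week, CV | No difference | Ratio 0.36 | Ratio 0.50 |
|---|---|---|---|
| 1, 0.6 | 6.0%, 4.7% | 93.2%, 95.6% | 66.0%, 74.3% |
| 1, 1.0 | 5.4%, 5.0% | 66.8%, 72.2% | 35.8%, 42.4% |
| 3, 0.6 | 5.8%, 4.6% | 98.9%, 99.5% | 82.5%, 89.1% |
| 3, 1.0 | 5.2%, 4.9% | 74.4%, 79.7% | 41.9%, 49.4% |
| 5, 0.6 | 6.5%, 5.1% | 99.5%, 99.8% | 86.1%, 91.8% |
| 5, 1.0 | 5.3%, 4.9% | 76.5%, 81.7% | 43.5%, 51.4% |

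The power loss is 0.3 to 5.4 points at ratio 0.36 and 5.7 to 8.3 points at ratio 0.50. Under no difference, the two-sided error is 5.2 to 6.5% against 4.6 to 5.1% with matched windows. All of the excess lies in the tail against RT-CGM (about 3.7 to 5.1%). Rejections in favour of RT-CGM fall from about 2.5% to 1.0 to 1.6%.

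**The case against.** The strongest reply is that no passage says the episodes will be compared as raw totals. Section 2 is a list of outcome names, and a count per day or per week would fit the same labels. That stands as a limit: the calendar mismatch is certain, but the distortion arises only if raw counts are used. It does not remove the point, because the text as written gives numbers, an unequal window and no denominator.

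Second, three ten-day sensors last 30 days, so 30 may be where the window came from and the mismatch may be loose drafting. That is plausible. But section 6.1 gives the block in weeks and does not start it before week 9; if an earlier start was meant, that text needs correcting instead.

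Third, the CGM insertion row in Appendix 1 is marked at visit 1 and at the end of each of weeks 1 to 11, with no arm named. It could be read as sensor wear in week 8 for everyone. Section 6.1 is specific to the SMBG arm, and Appendix 1 places the blinded downloads at weeks 2, 6 and 12, in line with that block schedule. The unlabelled row does not override it.

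Fourth, the effect is small, runs against the device, and concerns outcomes for which the plan claims no power. All of that is correct, and it sets the grade.

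**Conclusion.** The concern holds and is minor. The stated window does not fit the plan's own data schedule: 30 planned sensor days in RT-CGM against 28 in SMBG. At equal true rates and full wear, raw counts would be about 7% higher in RT-CGM. The consequence is a slightly understated benefit and a modest loss of power on one secondary outcome, or two if excursions are sensor-based. With full wear it does not raise the risk of a false finding in favour of RT-CGM.

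The two-day gap rests only on the documents and on reading weeks 9 to 12 as four whole weeks. The size of the effect on the test also rests on raw counts being compared, on the Wilcoxon test being the one used, and on the assumed episode rates, CVs and reductions.

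**What to change.** 1. In section 7, define the outcome window as weeks 9 to 12 (days 57 to 84) in both arms.
2. Analyse serious sensor episodes, and excursions if they are sensor-based, as each person's rate per week of valid sensor wear. Compare the arms with the Wilcoxon test that section 7 provides for non-parametric data.

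Either step alone removes the planned 30 v 28 imbalance. The first makes all sensor outcomes refer to the same days. The second also protects against unequal actual wear, which is a separate matter and not part of the size given above. If wear were 95% in one arm and 85% in the other (an assumption; the documents give no figure), raw counts over matched 28-day windows would differ by a ratio of 0.85/0.95 = 0.89 to 0.95/0.85 = 1.12. The simulated error would be 5.7 to 8.4%, against 4.7 to 5.7% with rates.

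Rates would help too if the section 7 sub-analysis of hypoglycaemia is meant to span the whole study rather than simply all hours of the day. Planned SMBG sensor days would then be 14 + 21 + 28 = 63 against 84, a ratio of 1.33.

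The cost is two RT-CGM days dropped from the window and a wear-time calculation per person. No visits, sensors or tests are added. With equal windows and full wear, every count is divided by the same four weeks, so the ranks and the Wilcoxon result are unchanged.

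### The planned tests ignore the randomisation stratum and, for HbA1c and the visit-1 scores, the visit-1 value; whether final values or changes are compared is not clearly fixed

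*Combined protocol and SAP*

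**What the plan says.** Section 6.1 of the combined protocol and SAP fixes one stratification factor: "Randomisation will be done using sealedenvelope.com and stratified by insulin delivery modality".

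Section 7 holds the whole analysis plan. For the primary, "The primary outcome will be assessed by two-tailed unpaired t-test". For the secondaries, "parametric data will be compared between the two study arms by two-tailed unpaired t-test for continuous variables", and otherwise "Non-parametric data will be compared using a Wilcoxon Rank sum test". It names no covariate, regression model or stratified test.

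On time windows, Section 7 has one statement for the start of the study, "Baseline data will be taken from the first 14 days of monitoring", and a second one for its end: "outcomes will be calculated from the last 30 days of the treatment period". Both statements fit sensor data.

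HbA1c and the Gold score are taken at clinic visit 1, as are "questionnaires (Diabetes treatment satisfaction questionnaire, CGM usability, PAID, and Fear of hypoglycaemia survey score (HFS2"). Section 6.1 describes all of these before it describes randomisation. Section 6.3 and Appendix 1 repeat HbA1c, the Gold score and the questionnaires at week 12.

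**The concern.** Two kinds of information are in hand before treatment starts, and no named test uses either.

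- **The stratum.** If insulin delivery modality predicts the outcome, leaving it out of the analysis gives away precision that the stratified design could deliver.
- **The visit-1 value.** For HbA1c, Gold score, PAID, HFS2 and treatment satisfaction, adjusting for the participant's own visit-1 value usually reduces the residual variance. Section 7 plans no such adjustment and does not clearly say whether week-12 values or changes from visit 1 are compared. Which is better depends on a correlation that the plan does not give. If the choice is left until the data are seen, it also becomes a route to false-positive results.

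The visit-1 part does not extend to the primary or the other sensor outcomes, whose only baseline comes after randomisation. Nor does it extend to CGM usability, which has no comparable baseline in participants new to CGM.

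The sample size was set for the primary alone, so the secondaries have no spare precision. Hypoglycaemia awareness, which the Gold score measures, is part of the stated aims and hypothesis.

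**Working it through.** **1. The plan's own figure.** Inputs from Section 7: means 2.1% and 5.8%, SDs 2.3% and 5.9%, two-sided 5%, 80% power.

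- Difference: 5.8 − 2.1 = 3.7 points.
- Root-mean-square SD: √[(2.3² + 5.9²)/2] = √20.05 = 4.48.
- Standardised difference: 3.7/4.48 = 0.826.
- Noncentral t: 24 per group gives 80.0% power and 25 gives 81.7%. Welch's form gives 79.1% and 80.8%, so 25 is the exact Welch answer.
- Drop-out: 50 × 1.10 = 55.

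The stated 25 per group and 55 in total reproduce.

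**2. Visit-1 outcomes.** Assumptions: 25 per group, effect 0.6 SD, equal SDs at the two visits, visit-1/week-12 correlation r. The documents give no r. Relative to final values, the variance is 2(1 − r) for changes and about 1 − r² for ANCOVA. Power for changes is therefore that of a standardised effect 0.6/√[2(1 − r)]; at r = 0.3 this is 0.6/1.183 = 0.507, giving 42.0%. The ANCOVA row is simulated (arm, visit-1 value and modality; 40,000 runs) and so includes the cost of estimating the covariate effects.

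| Power | r = 0 | 0.3 | 0.5 | 0.7 |
|---|---|---|---|---|
| Final values | 54.7% | 54.7% | 54.7% | 54.7% |
| Changes | 31.2% | 42.0% | 54.7% | 76.5% |
| ANCOVA | 53.5% | 57.8% | 65.9% | 82.0% |

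Against final values, ANCOVA changes the standard error by about +1, −3.5, −12 and −28%. Changes lose to final values at r = 0.3 and beat them at r = 0.7. ANCOVA is about 1 point below the better option at r = 0 and above both from r = 0.3.

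With ranks (a 7-category score cut from the same kind of data, an assumption), at r = 0.3, 0.5 and 0.7:

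| Power | r = 0.3 | 0.5 | 0.7 |
|---|---|---|---|
| Wilcoxon, final values | 51.0% | 50.5% | 50.0% |
| Wilcoxon, changes | 34.1% | 43.4% | 61.3% |
| Van Elteren by modality | 50.5% | 49.8% | 49.6% |
| Rank ANCOVA | 53.4% | 59.5% | 73.1% |

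Rank ANCOVA had type I error of 4.9 to 5.2%.

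**3. Leaving the choice open.** In simulation under no effect, the final-value and change tests each hold about 5%. Taking the smaller of the two p-values gives about 9% at r = 0.5 and 0.7 when modality has no effect. The final-value, change and ANCOVA estimates all centre on the true effect.

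**4. The stratum in the primary model.** Assumptions: 25 per group, planning means and SDs, normal data, 30% pump users, and R² as the share of mean within-arm variance explained by modality. The adjusted model is arm plus modality with HC2 (unequal-variance) standard errors; 60,000 runs per cell.

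| | R² = 0 | 2% | 5% | 10% |
|---|---|---|---|---|
| Balanced within strata: unadjusted | 81.6% | 81.8% | 81.9% | 82.6% |
| Balanced within strata: adjusted | 81.6% | 82.2% | 83.3% | 85.2% |
| No within-stratum balance: unadjusted | 81.6% | 81.9% | 81.5% | 81.6% |
| No within-stratum balance: adjusted | 80.7% | 81.8% | 82.6% | 84.5% |

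Type I error of the unadjusted test is 5.3, 5.0, 4.8 and 4.0% with balance and 5.1 to 5.4% without. HC2 runs at 5.0 to 5.6%. With 55 recruited, permuted blocks of 4, 10% random loss and R² = 10%, Welch has size 3.9 to 4.3% and power 81 to 82%. HC2 has size 5.3 to 5.5% and power 84 to 85%, so part of that gain is a difference in size.

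**5. How large R² can plausibly be.** With pump share 0.3 and an additive effect δ, 0.3 × 0.7 × δ² = R² × 20.05. If pump users have less hypoglycaemia, their CGM-arm mean is 2.1 − 0.7δ.

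- R² = 5%: δ = 2.18, mean 0.57%.
- R² = 10%: δ = 3.09, mean −0.06%.
- R² = 20%: δ = 4.37, mean −0.96%.

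A percentage of time cannot be negative, so under these assumptions values of 10% and above sit badly with the planning mean.

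**The case against.** **The planned tests are valid.** This stands. A reader might infer that ignoring the stratum biases the primary comparison or inflates its type I error, or that the trial is underpowered. The documents support none of these. Under randomisation each fixed comparison is unbiased, the unadjusted test holds its size or is conservative, and 25 per group reproduces.

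**The outcome window implies final values.** This stands in part. The words "outcomes will be calculated from the last 30 days of the treatment period", together with tests that compare the two arms and no mention of change, point to end-of-study values. But that sentence is written for sensor data, and HbA1c and the questionnaires are single measurements, so the question is not settled for them. On the final-value reading, the comparison with changes falls away and the gain of ANCOVA over final values remains.

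**The 9% is hypothetical.** This also stands. Nothing in the plan says that the choice will be made after seeing the data. The figure is a reason to close the gap and is no evidence of an inflated error rate.

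**The stratum gain is small and rests on assumptions.** Agreed. A reader might infer a substantial gain for the primary from a strongly prognostic modality. Step 5 shows why that is hard to reconcile with the planning figures. The conservatism of the unadjusted test also depends on balance within strata. Section 6.1 states no block size, and Section 7 expects losses ("To allow for a 10% drop-out 55 participants will be recruited").

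**These are secondary outcomes.** True, and the 0.6 SD effect is only illustrative. That limits the weight of the point but does not remove it.

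**Conclusion.** The point holds as an inexpensive improvement; no figure or planned test in the document is wrong. For any single analysis fixed in advance, the consequence is lost efficiency and not bias.

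The larger part concerns HbA1c, Gold score, PAID, HFS2 and treatment satisfaction. Relative to final values, visit-1 ANCOVA moves power by about −1, +3, +11 and +27 points at r = 0, 0.3, 0.5 and 0.7, for an assumed 0.6 SD effect. It also removes a choice that, if made after seeing the data, would carry a type I error of about 9%.

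The smaller part is the primary. Adding modality is worth about 0 to 2 points for R² up to 5% and perhaps 3 at 10%. Its main merit is that the analysis then follows the randomisation.

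Confidence is moderate, because r, R² and the pump share are not in the documents. The point also takes the visit-1 measures to precede randomisation. The order of the text in Section 6.1 indicates this but does not state it outright.

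**What to change.** **Main change.** For HbA1c, Gold score, PAID, HFS2 and treatment satisfaction, state that the week-12 value is the outcome and analyse it by ANCOVA on arm, visit-1 value and insulin delivery modality. Where ranks are needed, use rank ANCOVA (ranked week-12 value on arm, ranked visit-1 value and modality) and report the ANCOVA difference beside it, since the rank test gives no effect in score units. State that visit-1 measures are completed before allocation is known. Fix all this before any outcome data are seen.

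**Secondary change.** Analyse the primary with a linear model on arm plus modality with unequal-variance (HC2) standard errors, reporting the adjusted difference and 95% CI. Keep the unpaired t-test as a sensitivity analysis, stating whether it is the pooled or Welch form.

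**Not to do.** Do not adjust any outcome for CGM days 1 to 14: they follow randomisation, and adjustment could remove part of the treatment effect. A van Elteren test by modality is not worth adding, as it shows no gain over Wilcoxon in the runs above.

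**Cost.** SAP wording only: the covariates are already collected and the sample size is unchanged. The price is one or two degrees of freedom, up to about 1 point of power if the covariates are not prognostic, and an HC2 type I error slightly above nominal (5.0 to 5.6%). HC2 cannot be computed if a stratum holds a single participant, so a fallback should be named. Adjustment does not deal with skewness in the primary.

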1. INTRODUCTION

1.1 BACKGROUND

Type 1 diabetes (T1DM), which affects 300,000 in the UK, is characterised by autoimmune destruction of the pancreatic beta cells, leading to absolute deficiency of insulin. Management of T1DM requires exogenous insulin administration, aiming for glucose concentrations as close to physiological values as possible. Intensive management of T1DM improves glucose control and reduces the risk of microvascular diabetes complications and cardiovascular disease [1]. In the UK diabetes consumes more than 10% of the National Health Service budget [2] and in the USA a relatively greater amount is spent on type 1 compared with type 2 diabetes (8.6% of the diabetes budget compared with 5.6% of diabetes prevalence) [3]. Medication and insulin pump therapy accounts for less than 10% of diabetes expenditure with the majority of costs incurred in the treatment of complications [4].

Optimal control remains challenging to achieve and intensive insulin treatment increases the risk of severe hypoglycaemia, with lower glucose values also associated with an increased frequency and severity of moderate hypoglycaemia [5, 6]. Severe hypoglycaemia is defined as any episode of hypoglycaemia requiring the assistance of a third party actively to treat. Hypoglycaemia is associated with morbidity and even mortality, and places a financial burden on health systems.

Severe hypoglycaemia costs £13million per year in NHS costs [7]. Between 4 and 10% of deaths in people with type 1 diabetes are attributed to hypoglycaemia and the risk of severe hypoglycaemia increases 6-fold in people with impaired awareness of hypoglycaemia. Avoidance of hypoglycaemia is associated with restoration of hypoglycaemia awareness and this may be enabled by the use of continuous glucose monitoring.

In type 1 diabetes real-time continuous glucose monitoring (CGM) improves overall glucose control in all age groups when used continuously, reduces hypoglycaemia in people with an HbA1c <7.0%, and may reduce severe hypoglycaemia [8-10].

In England continuous glucose monitoring is supported by NICE for people with type 1 diabetes who are willing to commit to using it at least 70% of the time and to calibrate it as needed, and who have any of the following despite optimised use of insulin therapy and conventional blood glucose monitoring [11]:

- More than 1 episode a year of severe hypoglycaemia with no obvious preventable precipitating cause.

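### Severe hypoglycaemia and ambulance call-outs fall to a Wilcoxon test that would usually report medians of 0 against 0; a rate ratio with a confidence interval is a cheap improvement

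*Combined protocol and SAP*

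**What the plan says.** Section 2 lists "Severe hypoglycaemia" and "Ambulance call-out rates" among the secondary outcomes, with no denominator, time window or effect measure. Section 1.1 makes the first a discrete, repeatable event: "Severe hypoglycaemia is defined as any episode of hypoglycaemia requiring the assistance of a third party actively to treat".

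Section 7 gives one generic rule for secondary outcomes: "parametric data will be compared between the two study arms by two-tailed unpaired t-test for continuous variables", and then "Non-parametric data will be compared using a Wilcoxon Rank sum test". It specifies no count model, exposure term, rate ratio, confidence interval or proportion of participants with an event.

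Other text that bears on the point:
- Section 7 takes outcomes from the final 30 days. A sub-analysis also looks at hypoglycaemia outcomes over the whole period.
- Section 3.3 fixes follow-up at 12 weeks per participant, and section 7 allows for 10% drop-out.
- Section 4.4 permits discretionary withdrawal when glucose control worsens.
- Section 8.2 keeps participants who are moved to alternative treatment in follow-up and analysis.
- Section 6.1 stratifies randomisation by how insulin is delivered.

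**The concern.** The t-test is reserved for continuous variables. A count that is 0 for most people, with a few ones and twos, is not continuous, so on the plan's wording it goes to the rank test. The usual summary beside that test is a median per arm. With sparse events both medians are 0 even when the underlying rates differ several-fold.

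The two outcomes bear directly on the frequency and severity of hypoglycaemia named in the aims. As planned, a reader would probably receive a p-value for each and no estimate of how much the event rate changed. For an outcome that section 2 itself calls a rate, the stated methods estimate neither a rate nor a ratio of rates.

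**Working it through.** **1. The plan's own figure.** The only sample-size calculation is for the primary outcome: "and with 80% power, 25 participants would be needed in each group". Inputs from section 7: means 2.1 and 5.8, SDs 2.3 and 5.9, two-sided 5%.
- SD = √((2.3² + 5.9²)/2) = 4.478; difference = 3.7.
- n = 2 × (1.960 + 0.842)² × 4.478² / 3.7² = 23 per arm (24 with the t-distribution).
- At 25 per arm, power is 83.2% (normal) or 81.7% (t).

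The figure reproduces. No corresponding calculation exists for the event outcomes.

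**2. Assumptions for the event outcomes.** Control rates of 1, 2, 4 and 8 per person-year; rate ratio 0.36 (borrowed from the 64% reduction in the primary outcome); 25 per arm; variance μ + kμ², with k from 0 (Poisson) to 2. None of these comes from event data in the documents.

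**3. How often both medians are 0.** Mean count μ = rate × 84/365. P(no event) = e^(−μ) if k = 0, otherwise (1 + kμ)^(−1/k). The median of 25 is 0 when at least 13 people have no event. Example at 2 per year, k = 0:
- Control: μ = 2 × 84/365 = 0.460; P(0) = 0.631; P(Bin(25, 0.631) ≥ 13) = 0.911.
- CGM: μ = 0.36 × 0.460 = 0.166; P(0) = 0.847; P(at least 13) ≈ 1.000.
- Both medians 0: 0.911 × 1.000 = 91%.

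| Control rate/year | k | P(0) control | P(0) CGM | Both medians 0, exact | Simulated |
|---|---|---|---|---|---|
| 1 | 0 | 0.794 | 0.920 | ~100% | 100% |
| 2 | 0 | 0.631 | 0.847 | 91% | 91% |
| 2 | 2 | 0.722 | 0.867 | 99% | 99% |
| 4 | 0 | 0.398 | 0.718 | 15% | 13% |
| 4 | 2 | 0.593 | 0.775 | 83% | 84% |
| 8 | 2 | 0.462 | 0.656 | 33% | 34% |

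The problem is near-certain at 1 to 2 events per year and fades as events become common.

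**4. Power over 12 weeks (simulated, 25 per arm).** NB-LR is a negative binomial likelihood-ratio test.

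| Rate/year | k | t-test | Wilcoxon | NB-LR |
|---|---|---|---|---|
| 1 | 0 | 26% | 27% | 30% |
| 1 | 2 | 18% | 20% | 26% |
| 2 | 0 | 46% | 45% | 47% |
| 2 | 2 | 28% | 27% | 36% |
| 4 | 0 | 76% | 74% | 77% |
| 4 | 2 | 38% | 34% | 47% |
| 8 | 0 | 96% | 95% | 96% |
| 8 | 2 | 47% | 38% | 54% |

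The NB-LR test had a type I error of 4.6% to 7.0%, so part of its gain is inflated size. A permutation test of the rate ratio is the fairer comparator. At 0.3 v 0.1 events per 12 weeks its power was about equal to that of the planned tests (roughly 25% to 28% each). At 1 to 2 control events per 12 weeks with overdispersion it gained about 7 to 10 points over Wilcoxon and only 2 to 3 over the t-test.

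**5. Window.** At 2 per year, 25 controls yield 25 × 2 × 84/365 = 11.5 expected events over 12 weeks but 25 × 2 × 30/365 = 4.1 in 30 days. With k = 0, power falls from 46% to 17% (t-test) and from 45% to 19% (Wilcoxon). The window matters more than the test.

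**6. Unequal follow-up, no true effect.** If a fraction d of one arm leaves at uniformly distributed times, that arm's mean raw count is multiplied by 1 − d/2: 0.95, 0.90 and 0.85 for 10%, 20% and 30%. Type I error at 0% v 10% drop-out was 4.1% to 6.8% (t-test) and 4.3% to 6.5% (Wilcoxon). At 5% v 30% the worst case was 8.7% and 9.3%, against 3.9% with a follow-up offset. A separate run at similar drop-out gave 6% to 10% against about 5%.

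**7. Arms with no events.** At 0.1 events per 12 weeks with k = 1 and 28 people, P(no event in the arm) = 1.1^(−28) = 7%. In 30 days the mean is 0.1 × 30/84 = 0.036, and the probability is 1.036^(−28) ≈ 37%. Any rate-ratio analysis therefore needs a fallback.

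**The case against.** The strongest replies are these.

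- **Per-person raw counts are nowhere stated.** True. This is inferred from the generic rule, and an individual rate could be ranked instead. Ranking rates would take account of days observed but would still give no rate ratio, and with mostly zero values the medians would still be 0.
- **A t-test would give a usable estimate.** True. With fixed follow-up, a difference in mean counts is a rate difference per 12 weeks with an interval. The lack of an effect size belongs to Wilcoxon. The t-test is, however, limited by section 7 to continuous variables.
- **A reader might infer a serious loss of power.** The figures do not support that. For rare events the tests are about equal, and the shortage of events is the main limit.
- **A reader might infer that drop-out will pass for a treatment effect.** Follow-up is fixed at 12 weeks, section 8.2 retains participants whose treatment is changed, and inflation is small at the planned 10%. Under the 30-day rule, someone lost early has a missing outcome and not necessarily a low count. The direction of the bias in raw counts over the whole period stands; a material size needs something like 5% v 30%.
- **A model brings its own problems.** Also true: inflated size in small samples, arms with no events, and stratified randomisation. An offset corrects unequal person-time but not withdrawal related to the outcome under section 4.4. These shape the fix and do not remove the need for it.

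**Conclusion.** The point holds as a cheap improvement to a secondary analysis. Section 7 routes two sparse event outcomes to a rank test that, at assumed control rates of 1 to 2 per person-year, would report medians of 0 v 0 in 91% to nearly 100% of trials with a rate ratio of 0.36, and no rate ratio. Across the rates tried, the benefit of a rate analysis is the estimate and its interval. The power gain over Wilcoxon is negligible for rare events and about 7 to 10 points for frequent, overdispersed ones. Protection against false positives matters only with large differential drop-out.

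All of this rests on assumed rates, overdispersion and drop-out patterns. If events were as common as 4 or more per year with little overdispersion, the medians would mostly not both be 0 and the case would be weaker. The documents do not support the stronger readings that the planned tests are invalid or that the trial's main conclusion is at risk.

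**What to change.** In section 7, for severe hypoglycaemia episodes and ambulance call-outs:

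1. Analyse events over the full 12 weeks, and say so explicitly, because the general rule is the final 30 days.
2. Fit a negative binomial model (or Poisson with robust variance) with log days observed as offset, counting events up to last contact.
3. Report the rate ratio with 95% confidence interval and, for each arm, total events, person-time and the number with at least one event.
4. Take the p-value from a permutation test of the rate ratio within the insulin-modality strata.
5. If an arm has no events or the model does not converge, report the counts and an exact or permutation comparison only.
6. State that the offset does not correct for withdrawal prompted by worsening glucose control.

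The cost is a few lines of text and standard software. The data needed are event counts, last-contact dates and the stratum. The downside is that the interval will be wide, and may not be estimable, if events are few. The primary analysis and the recruitment target of 55 do not change.
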